1.3 Research Hypothesis

1. The accuracy of AI-based cephalometric analysis is comparable to the conventional manual cephalometric tracing method.
2. The reliability of AI-based cephalometric analysis is better than the conventional manual cephalometric tracing method.

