3.0 Materials and Methods

3.1 Study Population

This prospective study includes 40 cephalometric radiographs of orthodontic patients seen in Orthodontic Specialist Clinic of Kulliyyah of Dentistry, IIUM Kuantan.

The sample size calculation was done with a significance level of 0.05 and a power value of 95%. A sample of a minimum of 37 radiographs was needed.

3.2 Inclusion criteria:

- Pretreatment OR post-treatment lateral cephalometric radiographs
- Orthodontic patients treated at the Orthodontic Specialist Clinic, IIUM
- Radiographs obtained between January 2023 and June 2023
- High-quality cephalograms without flaws affecting anatomical landmark positions

3.3 Exclusion criteria:

- Patients with surgical rigid fixations visible on radiographs
- Presence of orthodontic appliances on radiographs
- Presence of dental prostheses on radiographs
- Patients with syndromes and craniofacial deformities.

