3.5 Data Analysis

The mean, standard deviation, and standard error of the difference between the repeated measurements for each method and between the two methods will be calculated. The reliability of each method will be defined using the Pearson correlation coefficient (r^2). The level of statistical significance will be set at $P < 0.05$.

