4.0 Expected Outcome

Table 2: Angular and Linear Measurement of Cephalometric Values

Measurements	AI-based (WeDoCeph)			Manual			P-value
	Mean	S.D	r²	Mean	S.D	r²	
SNA (°)	n	n	n	n	n	n	n
SNB (°)	n	n	n	n	n	n	n
ANB (°)	n	n	n	n	n	n	n
FMPA (°)	n	n	n	n	n	n	n
MMPA (°)	n	n	n	n	n	n	n
UIA (°)	n	n	n	n	n	n	n
LIA (°)	n	n	n	n	n	n	n
IIA (°)	n	n	n	n	n	n	n
A-N perpendicular (mm)	n	n	n	n	n	n	n
POG-N perpendicular (mm)	n	n	n	n	n	n	n
ANS-Me perpendicular (mm)	n	n	n	n	n	n	n
SN (mm)	n	n	n	n	n	n	n
LFH (mm)	n	n	n	n	n	n	n
UFH (mm)	n	n	n	n	n	n	n
MxPI (mm)	n	n	n	n	n	n	n
MnPI (mm)	n	n	n	n	n	n	n

Table 3: Intraclass Correlation Coefficient

Intraclass Correlation	95% Confidence Interval			F Test with True Value 0			
	Lower Bound	Upper Bound	Value	df1	df2	sig	
Single Measures							
Average Measures							

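### Reliability is defined by a correlation that depends on film spread as well as tracing error, so the 16 values cannot be compared across parameters and the size and detectability of an AI-manual gap vary with spread

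*Combined protocol and SAP*

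**What the plan says.** Section 3.5 names one statistic as the definition of reliability: "The reliability of each method will be defined using the Pearson correlation coefficient (r^2"). Table 2 in section 4.0 gives r² a column under each method for all 16 parameters (8 angular, 8 linear).

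The sentence before it also plans an absolute measure: "The mean, standard deviation, and standard error of the difference between the repeated measurements for each method". Section 3.5 does not call this reliability. It has no clearly labelled place in Table 2, where the S.D column could mean the repeat differences or the raw values.

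Section 4.0 adds a shell headed "Table 3: Intraclass Correlation Coefficient". Section 3.5 does not mention an ICC, and the shell names no model, method or parameter.

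The second hypothesis in section 1.3 is a contrast between methods: "The reliability of AI-based cephalometric analysis is better than the conventional manual cephalometric tracing method". No test of that contrast is specified. Section 3.4 provides two readings per method, four weeks apart, on 40 films. The case mix is set by sections 3.2 and 3.3: "Pretreatment OR post-treatment lateral cephalometric radiographs" are pooled, and syndromes and craniofacial deformities are excluded.

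**The concern.** The second objective asks which method repeats its own measurements more closely. A correlation answers a different question: how large the repeat error is relative to the differences between these particular films. The same tracing error gives a low value on a parameter that varies little between patients and a value near 1 on one that varies a lot. A different mix of pre- and post-treatment films would change every value with no change in tracing.

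This is separate from a correlation's blindness to a constant shift between sessions. Moving to an ICC would not remove it, because an ICC is also a ratio involving between-film variance.

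At stake is how Table 2 is read. Differences between rows would partly reflect anatomy, and the apparent size of any AI advantage would partly reflect case mix.

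**Working it through.** **Inputs from the documents.** 40 films, two readings per method, significance level 0.05, 16 parameters. The plan's own sample-size figure, "A sample of a minimum of 37 radiographs was needed", cannot be reproduced because no effect size, SD or test is given. This point does not rest on it.

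**Inputs assumed.** Between-film SD s_T and single-reading error SD s_e, in degrees or mm. The documents give neither, so ranges are shown.

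**Step 1: same error, different spread.** With equal error variance at both readings, r = s_T² / (s_T² + s_e²), and the SD of the repeat difference is s_e × √2. With s_e = 1:

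| s_T | r | r² | SD of repeat difference |
|---|---|---|---|
| 1 | 1/2 = 0.50 | 0.25 | 1.41 |
| 2 | 4/5 = 0.80 | 0.64 | 1.41 |
| 2.5 | 6.25/7.25 = 0.86 | 0.74 | 1.41 |
| 4 | 16/17 = 0.94 | 0.89 | 1.41 |
| 10 | 100/101 = 0.99 | 0.98 | 1.41 |

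The correlation moves with spread, while the repeat-difference SD does not.

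**Step 2: the printed AI-manual gap.** Take error SD 1 for AI and 1.5 for manual. The Fisher z of r is ½ ln(1 + 2 s_T²/s_e²).

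| s_T | r, AI | r, manual | gap in r | gap in r² | gap in Fisher z |
|---|---|---|---|---|---|
| 1 | 0.500 | 0.308 | 0.192 | 0.155 | 0.549 − 0.318 = 0.231 |
| 2.5 | 0.862 | 0.735 | 0.127 | 0.202 | 1.301 − 0.940 = 0.361 |
| 10 | 0.990 | 0.978 | 0.012 | 0.024 | 2.652 − 2.249 = 0.403 |

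On the scale Table 2 prints, the gap nearly vanishes at wide spread. On the Fisher z scale, which governs detectability, it shrinks at narrow spread.

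**Step 3: power.** Simulation with 40 films, 20,000 data sets, true film values shared by both methods, error SD 1 against 1.5, two-sided 0.05:

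| s_T | Contrast of dependent correlations | Pitman-Morgan test on repeat differences |
|---|---|---|
| 1 | about 20% | about 70% |
| 2.5 | about 52% | about 70% |
| 10 | about 68% | about 70% |

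With equal error in both methods, each test rejected in about 5% of data sets.

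**Step 4: if the automatic method repeats almost exactly.** Section 3.4 describes automatic landmarking. If re-upload returned nearly identical values (an assumption), AI r² would be near 1 and the apparent advantage would be 1 minus manual r². From Step 1, with manual error SD 1, that is 1 − 0.64 = 0.36 at spread 2 and 1 − 0.98 = 0.02 at spread 10, for the same manual error.

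**The case against.** The strongest reply is that the second objective compares AI with manual within each parameter on the same films, so spread affects both methods alike. No ranking across parameters is planned. Much of this stands. With errors of 1 and 1.5, the correlations order the methods correctly in about 98% of simulated data sets at spread 2.5 and 99% at spread 10. What does not survive is the size of the gap, or the power at narrow spread.

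A second reply is that the plan already computes the SD of the repeat difference for each method, and the S.D column of Table 2 may be meant for it. That is fair. A correlation is the only statistic named as the definition of reliability, but it is not the only repeat-measurement statistic planned. The change is therefore largely one of definition and labelling.

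A third reply is that relative and absolute reliability are both legitimate definitions. That is true in general, but a claim that one method has less repeat error than another calls for the absolute one.

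Readers might also infer more than the documents support:

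- That narrow-range parameters would be declared unreliable. The plan states no cut-off, grade or label.
- That values near 1 make a real difference undetectable on wide-range parameters. They make it look small, but at spread 10 power is about 68% against about 70%, so almost nothing is lost.
- That power is as low as 30% to 37% at spreads of 2.5 to 10. Those figures come from treating the two correlations as independent, which the plan does not specify. With a false-positive rate of about 1%, such a test is very conservative here.

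**Conclusion.** The point holds as a defect in the definition of reliability. That each r, r² or ICC depends on film spread is algebraic and needs no assumption about size, so the 16 values should not be read against one another. The size of an AI-manual gap within a parameter also depends on spread: compressed in print on wide-range parameters, and harder to detect on narrow-range ones.

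The loss of power is material only where between-film SD is not much larger than tracing error: from about 70% to about 52% at spread 2.5, and to about 20% at spread 1. These figures assume error SDs of 1 and 1.5, and none of the SDs is in the documents.

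A reader might go further and infer that film spread could reverse the order of the methods. It does not do so in expectation, because both methods use the same films, and in samples of 40 the order is usually preserved.

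**What to change.** In section 3.5, make the primary reliability measure for each parameter and method the within-film error SD, s_w = SD of the repeat difference / √2, in degrees or mm. Give its 95% CI and the repeatability coefficient, 1.96 × √2 × s_w. Report the planned mean repeat difference beside it, because the SD of differences does not show a constant shift between sessions.

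Compare AI with manual in each parameter by a paired-variance (Pitman-Morgan) test on the repeat differences. State in advance that if AI repeat error is zero or near zero, each s_w will be reported with its CI in place of a ratio, which would then be uninformative.

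Label the Table 2 columns accordingly. Keep r, or an ICC with its model stated, as secondary and not for comparing parameters.

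The cost is wording in section 3.5 and relabelled columns. The two readings per method and the repeat-difference SD are already planned, so no new data are needed. Comparison with papers that report only correlations becomes slightly less direct, which keeping the correlation as secondary covers.

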2.3 Evaluation of The Accuracy and Reliability of Automated Cephalometry Analysis Software

A study by Anuwangnukroh et al. (2018) evaluated the reliability of the cephalometric analysis using the dental imaging software (Carestream Dental). They found that the automated cephalometric analysis software has significant difference of more than 2 degrees when compared to the manual hand-based analysis. They also found that the differences come mainly from the angular parameters.

On the other hand, another study by Katyal et al., (2022) investigated the automated tracing software using the WebCeph software. They found there is no significant difference in the skeletal, dental and the soft-tissue parameters between the two methods. However, it takes shorter time for the automated tracing to analyse the data when compared to the manual tracing where the time taken is 30.2 ± 6.4 s and 472 ± 40.4 s respectively (Katyal et al., 2022). Another study by Tsolakis (2022) compared the digital automatic method and digital manual method of cephalometric analysis and found small difference between the two methods but it was not clinically significant.

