3.4 Methodology

Ethical approval will be obtained before the commencement of the study. Forty cephalometric radiographs will be selected. Calibration will be done prior to landmark identification to ensure agreement between the examiners.

For manual tracing, 18cm x 24cm of radiographic film images of lateral cephalograms will be obtained and traced manually on a view box using transilluminated light under dark room. Each cephalograms will be secured over the view box first, and then a sheet of matte acetate tracing paper sized 22cm x 28cm are taped over the radiographic film. Three orientation marks will be placed as a reference point over the film and the tracing paper. After that, hard and tissue landmarks will be traced onto the tracing paper manually using a HB pencil. A total of 11 anatomical landmarks will be plotted on each cephalograms which are the A point (subspinale, or A), B point (B), sella (S), nasion (N), orbitale (O), porion (Po), anterior nasal spine (ANS), posterior nasal spine (PNS), gonion (Go), menton (Me) and pogonion (Pog).

Measurements of the cephalometric parameters (8 angular and 8 linear) will be taken with the help of millimetre ruler and a protractor. All measurements will be performed twice by the same investigator with intervals of 4 weeks from the first measurements. Angular measurements ($^{\circ}$) include the SNA, SNB, ANB, FMPA, MMPA, UIA, LIA, IIA. While the linear measurements (mm) include the NA, NPog, ANS-Me, SN, LFH, UFH, MxPI, MnPI.

Table 1: Definition of the relevant cephalometric points

Cephalometric points	Definition
Point A (A)	The deepest point in the concavity of the anterior maxilla between the ANS and alveolar crest
Point B (B)	The deepest point in the concavity of the anterior mandible between the alveolar crest and Pog
Sella (S)	The midpoint of sella turcica
Nasion (N)	Junction of the frontal and nasal bones at the frontonasal suture
Orbitale (O)	The most inferior point on the infra- orbital margin
Porion (Po)	The most superior point of the external auditory meatus
Anterior Nasal Spine (ANS)	The anterior limit of the nasal floor
Posterior Nasal Spine (PNS)	The posterior limit of the nasal floor
Gonion (Go)	The most posterior and inferior point on the angle of the mandible
Menton (Me)	The most inferior point on the bony chin
Pogonion (Pog)	The most anterior point on the bony chin

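### Hypothesis 1 claims the AI is comparable to manual tracing, but section 3.5 sets no acceptable difference, limits of agreement or decision rule, and no P-value in the planned tables can stand in for them

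*Combined protocol and SAP*

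**What the plan says.** All references are to the combined protocol and SAP.

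- Section 1.3, Hypothesis 1: "The accuracy of AI-based cephalometric analysis is comparable to the conventional manual cephalometric tracing method". Research question 1 in section 1.2 asks the same thing.
- Section 3.5 plans the mean, SD and "standard error of the difference between the repeated measurements for each method and between the two methods will be calculated". It assigns the Pearson correlation to the reliability of each method and ends with the significance level: "The level of statistical significance will be set at $P < 0.05". It names no test.
- Section 4.0, "Table 2: Angular and Linear Measurement of Cephalometric Values", has 16 rows (8 angular, 8 linear). Each row has a mean, SD and r² per method, then a single P-value.
- Section 4.0, Table 3, is a shell for an intraclass correlation with confidence bounds and an "F Test with True Value 0". Section 3.5 does not mention it. Its comparison (repeat readings or AI against manual), type and acceptance threshold are not given.

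No section states an acceptable difference, an equivalence margin, limits of agreement, an ICC cut-off, or how 16 results combine into one verdict on Hypothesis 1.

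**The concern.** A claim that two methods are comparable needs a statement of how much disagreement is tolerable and a rule for judging the data against it. The plan has neither. When the results arrive, the verdict on the first hypothesis would have to rest on the P-value or on a threshold chosen after the data are seen.

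The P-value can mislead in both directions. A noisy parameter can escape significance while individual radiographs differ widely. A precisely measured one can be significant over a trivial bias. The software would be used on individual radiographs, so the spread of individual differences matters as well as the mean.

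**Working it through.** **1. Does the plan's own number imply a margin?** Section 3.1 gives a significance level of 0.05, power of 95%, a minimum of 37 radiographs and 40 planned. It gives no test, effect size, SD or margin, so 37 cannot be reproduced forward. Working backwards (two-sided):

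- A paired t-test with n = 37 and 95% power corresponds to a standardized difference of 0.609.
- A test of correlation against 0, with n = ((1.960 + 1.645)/atanh r)² + 3 = 37, corresponds to r = 0.550.

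Different designs fit the same number, so it neither reveals nor implies an acceptable difference.

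**2. What could the P-values show?**

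- *Difference test (the reading the Table 2 layout suggests).* The null is a mean difference of 0. Failing to reject it is not evidence of agreement, and rejecting it says nothing about clinical size.
- *Correlation against 0.* Two methods can correlate perfectly with a constant offset.
- *ICC against 0 (Table 3).* Rejection rules out only an ICC of 0.

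**3. How far can a difference test depart from comparability?** Assumed: two-sided paired t-test at 0.05, n = 40, normal differences. The documents give no SD of AI-minus-manual differences, so a range is shown (degrees or mm).

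- Non-significance comes from the noncentral t with 39 df and noncentrality (bias/SD) × √40.
- Share of radiographs differing by more than 2 units at zero bias = 2 × (1 − Φ(2/SD)).
- Limits of agreement at zero bias = ±1.96 × SD.

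| SD | Non-significant, bias 0 | Non-significant, bias 1 | Non-significant, bias 2 | Beyond 2 units, bias 0 | Limits, bias 0 |
|---|---|---|---|---|---|
| 2 | 95% | 13% | <0.1% | 32% | ±3.9 |
| 2.5 | 95% | 31% | 0.15% | 42% | ±4.9 |
| 3 | 95% | 46% | 1.6% | 50% | ±5.9 |
| 4 | 95% | 66% | 13% | 62% | ±7.8 |
| 5 | 95% | 77% | 31% | 69% | ±9.8 |

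Example: at SD 3, 2 × (1 − Φ(0.667)) = 0.505, and 1.96 × 3 = 5.88.

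In the other direction, a bias of 0.5 is significant 87% of the time at SD 1 (noncentrality 0.5 × √40 = 3.16) and 54% at SD 1.5.

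**4. What precision does n = 40 give the alternative?** With t(0.975; 39) = 2.023:

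- 95% CI for the bias: ±2.023/√40 = ±0.32 SD.
- 95% CI for each limit: ±2.023 × √(1/40 + 1.96²/78) = ±0.55 SD.

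At SD 3 these are ±0.96 and ±1.65 units.

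**The case against.** The strongest reply is that section 3.5 already plans the mean and SD of the between-method difference, from which bias and limits of agreement follow, and that specific objective 1 in section 1.4.2 is only to investigate accuracy. This stands in part: the planned estimates do partly serve the objective. They do not give the hypothesis a basis, because the plan neither commits to the limits nor supplies a bound to judge them against.

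Two further points stand. Every SD in the illustration is assumed; the logical gap does not depend on them, but its practical size does. And a wide AI-minus-manual spread may partly reflect manual tracing error, so any bounds should take account of manual repeatability.

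Several stronger readings are tempting but not supported:

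- *That the plan will treat non-significance as comparability.* It does not say so; it simply states no other basis.
- *That Table 2's P-value is a difference test.* This is an inference from the layout, since no test is named. The conclusion survives the other readings in step 2.
- *That section 2.3 recognizes the gap or sets a bound.* It reports one earlier study as finding "no significant difference in the skeletal, dental and the soft-tissue parameters between the two methods" and says another "found small difference between the two methods but it was not clinically significant". These summarize separate studies. The 2 degrees mentioned there is likewise another study's result, not a limit adopted here.
- *That a 2-unit bias would routinely be missed.* At n = 40 this is a material risk only for noisier parameters: 1.6% at SD 3, but 13% at SD 4 and 31% at SD 5.

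**Conclusion.** The concern holds. The plan has no valid pre-stated basis for concluding that the AI is comparable to manual tracing, and neither the Table 2 P-value nor Table 3's test against 0 can provide one. The defect lies in the conclusion, not in the planned estimates of bias and spread.

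The gap itself follows from the text alone. Its illustrated size rests on a paired t-test, n = 40, normal differences and assumed SDs. It should be fixed before analysis, because it affects the first hypothesis and because bounds set after seeing the data lose their value.

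**What to change.** In section 3.5 and Table 2, replace the P-value as the basis for Hypothesis 1:

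1. For each parameter, report the mean AI-minus-manual difference with its 95% CI and the Bland-Altman 95% limits of agreement with their CIs. State which readings are compared, since each method is read twice, for example first AI reading against first manual reading of the same radiograph.
2. Before analysis, the investigators pre-state and justify acceptable bounds for each parameter, for bias and for individual differences. They should take into account the manual repeat differences that section 3.5 already plans, and say whether the point limits or their outer CIs decide.
3. Call a parameter comparable only if it meets its bounds. Otherwise report it as *not shown comparable*.
4. Either restate Hypothesis 1 by parameter, or pre-state which or how many of the 16 parameters must meet their bounds for an overall claim.
5. State what Table 3's ICC compares and its type, and do not use its test against 0 as evidence of comparability.

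The linear parameters are labelled differently in section 3.4 and Table 2. That is a separate point, not part of this one.

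**Cost.** Changes to the analysis text and table shells, and the work of justifying bounds. No new data are needed if *not shown comparable* is accepted as a result. At n = 40 noisier parameters may end there, given CIs of about ±0.32 SD for the bias and ±0.55 SD for each limit.

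### Sixteen parameters are each tested at P < 0.05 with no primary parameter and no rule combining them, so 0.05 is not the error rate of the answer to Hypothesis 1

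*Combined protocol and SAP*

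**What the plan says.** Section 1.3 states Hypothesis 1 as one claim about the method: "The accuracy of AI-based cephalometric analysis is comparable to the conventional manual cephalometric tracing method". Section 3.4 lists 16 outcomes: "Measurements of the cephalometric parameters (8 angular and 8 linear) will be taken" from every film. In section 4.0, "Table 2: Angular and Linear Measurement of Cephalometric Values" has one row per parameter and one P-value column, which makes 16 P-values.

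On the decision rule, section 3.5 offers only this: "The level of statistical significance will be set at" P < 0.05. It also plans the mean, SD and standard error of the between-method difference. It does not name the test behind the P-values, a primary parameter, a multiplicity rule or an agreement margin.

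Section 3.1 adds that "The sample size calculation was done with a significance level of 0.05 and a power value of 95"%, and that "A sample of a minimum of 37 radiographs was needed"; 40 are planned. Neither figure is tied to a parameter, an effect size or a test.

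**The concern.** The hypothesis is one statement and the evidence is 16 separate tests. Nothing says whether all rows, most rows or particular rows must agree. This leaves two errors uncontrolled.

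- **False difference.** With 16 chances at 0.05, a study of two methods that truly agree on average can easily show a significant row somewhere.
- **False comparability.** With mixed results, the authors can decide after seeing the data whether the agreeing or the disagreeing rows answer the hypothesis. If P > 0.05 is read as agreement, real differences that the study was too small to detect count in favour of the AI method. For a comparability claim this is the more harmful error.

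The rows are also not separate pieces of evidence. ANB is by geometry essentially SNA minus SNB, and all rows come from the same films.

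**Working it through.** **Inputs from the documents.** 16 parameters (section 3.4, Table 2); threshold 0.05 (section 3.5); 40 films, minimum 37, alpha 0.05, power 95% (section 3.1).

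**Assumptions.** A two-sided paired t-test on each row, since each film is measured by both methods but no test is named. No true AI-manual difference on any row. A common correlation between the rows' AI-manual differences, taken from 0 to 0.9 because none is given.

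**1. The plan's own figure.** The minimum of 37 cannot be reproduced forwards, because no effect size, SD or test is stated. Solved backwards for 95% power at two-sided 0.05, 37 fits a paired t-test with a standardised difference of 0.61. It equally fits a correlation of 0.55, or two independent groups of 37 with a difference of 0.84 SD. None of these is confirmed. The 0.61 is used below only to show cost.

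**2. False-difference rate, independent rows.** P(at least one of k rows below 0.05) = 1 − 0.95^k.

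- k = 16: 1 − 0.95^16 = 0.560
- k = 15 (ANB dropped): 1 − 0.95^15 = 0.537
- k = 14: 0.512; k = 13: 0.487

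**3. False-difference rate, correlated rows.** Simulation of 16 paired t-tests with n = 40:

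| Common correlation | At least one false row |
|---|---|
| 0.2 | 52% |
| 0.25 | 50% |
| 0.3 | 48% |
| 0.5 | 38% |
| 0.7 | 27% |
| 0.9 | 15% |

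The rate crosses one half at a correlation of about 0.25. Two or more false rows occur in about 15% to 19% of studies for correlations from 0 to 0.7.

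Modelling only structural links gives 51% to 54%. The links are ANB as SNA minus SNB, the interincisal angle as a function of the two incisor angles and MMPA, and LFH either the same as ANS-Me or separate. Adding a shared correlation of 0.3 lowers this to 43% to 47%. The incisor and LFH links are assumptions, because the documents do not define those measures.

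**4. What a split of alpha would do.** 0.05/16 = 0.0031. For the assumed 0.61 SD difference in one row:

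| Films | Power at 0.05 | Power at 0.0031 |
|---|---|---|
| 37 | 95% | 70% |
| 40 | 96% | 75% |

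**5. Why a split does not protect a comparability claim.** For illustration, take a true bias of 2 units, 40 films and an assumed SD of the paired difference of 4 or 6. The chance that the bias is not significant is 13% (SD 4) or 46% (SD 6) at 0.05. At 0.0031 it is 49% or 83%. A stricter threshold makes it easier to miss a real bias and call the methods comparable.

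**The case against.** The strongest reply has three parts.

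First, a reader might infer that a false difference somewhere is more likely than not, or that a study run as written would usually show one. The documents do not support that. It needs near-independent rows, with a common correlation below about 0.25. The documents give no correlation, and the rows share films and landmarks. This part of the reply stands: the supportable statement is well above 5%, and up to about 56% under independence.

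Second, a falsely significant row counts against Hypothesis 1, so the family-wise rate is not the error rate of the claim the study hopes to make. This also stands in part. The harmful error is false comparability, and its main source is the missing margin. But a margin alone would not say which of the 16 rows must meet it, so the missing primary set and combining rule remain a defect in their own right.

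Third, Table 2 commits the authors to showing every row. That limits selective reporting but not selective emphasis, because nothing fixes what a mixed table means.

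Two smaller points are fair. Manual angles are read with a protractor, so manual ANB need not equal SNA minus SNB exactly. And dropping ANB moves the independent figure only from 56% to 54%, so redundancy of that row is a minor part of the problem.

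**Conclusion.** The point holds. The plan has 16 P-values, one unadjusted threshold, no primary parameter and no route from the rows to an answer on Hypothesis 1.

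Under the assumptions above, the false-difference rate runs from about 15% (correlation 0.9) to 56% (independence). That is at least about three times the nominal 5% everywhere in that range, but it is not shown to exceed one half. It applies only if there is no true difference on any row.

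The rate of false comparability cannot be calculated at all, because no criterion for comparability is stated. The gap should be closed before data are read, since a rule chosen afterwards cannot restore control. It does not by itself invalidate the measurements or the planned descriptive results.

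**What to change.** In section 3.5, before any film is read:

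1. **Name a small primary set** containing angular measures and at least one linear measure, all constructible from the 11 listed landmarks. SNA, SNB and MMPA meet the landmark condition, but as a set they omit every linear measure and could not show a uniform scale error. SN is one linear measure the listed points define. The choice is the investigators'.
2. **State the criterion.** Claim comparability only if, for every member of the set, the confidence interval for the mean AI-manual difference lies within a margin the investigators fix in advance and justify. State the interval level. Because all members must pass, alpha need not be split. P > 0.05 must not serve as the criterion.
3. **Report the remaining rows** as mean differences with 95% confidence intervals and no significance claim. If a difference is claimed on any of the 16 rows, apply Holm across the 16 for that claim only, never to support comparability.
4. **Note in Table 2** that ANB is essentially SNA minus SNB and is not separate evidence.

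The cost is a few sentences in section 3.5 and extra columns in Table 2, with no new films. The downside is that fewer rows can carry a claim. Where Holm is used, power at its first step falls as shown in the working: from 95% to about 70% with 37 films, and from 96% to about 75% with 40, for the assumed 0.61 SD difference. Whether 40 films are enough for the interval criterion depends on the margins and on the SD of the differences, neither of which the documents give. This should be checked once the margins are set.
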